## 2.4 Sample Size

Using a two-sided paired t-test at significance level of 0.05, a sample size of 44 evaluable subjects provides 90% power to detect a mean paired difference in capture rate that is half of the standard deviation of the paired difference. For example, if the standard deviation of paired difference in capture rate is 10%, a sample size of 44 provide 90% power to detect a mean paired difference of 5% (PASS 2019). Approximately 50 subjects will be enrolled to obtain 44 evaluable subjects.

## 2.5 Interim Analyses

Not applicable.

## 2.6 Study Procedure

See protocol Section 1.2 and Section 7.

## 2.7 Endpoints

### 2.7.1 Primary Endpoints

Primary endpoint is capture rate following void (captured as % of urine captured by device and collected in canister, measured by weight), PureWick™ Male (System) compared with Stryker/ Sage PrimoFit™.

## 2.7.2 Secondary Endpoints

### Secondary Endpoint with Hypothesis Test:

capture rate following void (captured as % of urine captured by device and collected in canister, measured by weight), PureWick™ Male (System) compared with Stryker/ Sage PrimoFit™, in subjects that are unable to use traditional sheath style condom catheters. This hypothesis-testing is performed conditional on the success of the primary hypothesis-testing.

### Secondary Endpoints without Hypothesis Test:

- Overall Comfort score on a 5-point Likert scale (brief questionnaire)
- Ease of use score on a 5-point Likert scale (brief questionnaire)

## 2.8 Acceptance Criteria

Successful rejection of the Null hypothesis will provide evidence to support the superiority of PureWick™ Male (System) over the comparator device.

## 3 Intended Statistical Software and Data Information

### 3.1 Intended Statistical Software

SAS Version 9.4 (SAS Institute, Cary, NC) or above will be used to perform analyses and generate outputs.

### 3.2 Data Information

Analysis datasets and a document outlining the specification of analysis datasets will be stored in a version-controlled environment.

## 4 Analysis Population Set(s)

### 4.1 Population Definitions

The following populations are defined:

Population	Description
Enrolled	All participants who sign the ICF.
Intent-to-Treat (ITT)	Enrolled and randomized participants.
Per-Protocol	ITT subjects who are without major protocol deviation.
ITT Subpopulation	ITT subjects who are deemed unable to use traditional sheath style condom catheters.

ITT population will be used for the primary endpoint analysis. ITT subpopulation will be used for the secondary endpoint *with* hypothesis test. Per-protocol analyses may be performed as a sensitivity analysis.

## 5 Statistical Analysis/Calculations

### 5.1 Derived Variables

- Subject who are deemed unable to used traditional sheath style condom catheters:  
Answered “No” to “Is the participant’s anatomy compatible with traditional sheath-style condom catheters?” on Case Report Form (CRF) page entitled Professional Anatomical Compatibility.
- Capture rate:  
Captured urine weight / (captured urine weight + leaked urine weight), where
  - Captured urine weight is defined as canister final weight (g) - canister starting weight (g), and
  - Leaked urine weight is defined as pad final weight (g) - pad starting weight (g).
 A void of which (captured urine weight + leaked urine weight) < 10 g is considered not evaluable for the purpose of analyzing primary endpoint and secondary endpoint with hypothesis-testing.

### 5.2 Analysis Methods

#### 5.2.1 General Considerations

Study-wise Type I error is controlled using the Fixed Sequence method. The primary endpoint and a secondary endpoint are tested sequentially. The secondary hypothesis will be carried out, only if the primary hypothesis test is successful. Otherwise, the test for the secondary endpoint is considered exploratory.

#### 5.2.2 Primary Endpoint

The primary endpoint will be evaluated against the following hypotheses:

**H0:** Capture rate of PureWick™ Male (system) = Capture rate of established comparator (Stryker/ Sage PrimoFit™)

**H1:** Capture rate of PureWick™ Male (system) ≠ Capture rate of established comparator (Stryker/ Sage PrimoFit™)

A two-sided paired t-test will be used to test the hypotheses and p-value will be derived. A p-value < 0.05, combined with a capture rate in favor of PureWick™, indicates that PureWick™ is superior to PrimoFit™ in terms of urine capture.

An exploratory analysis will be performed using regression, where subject may be included as the random effect, and period, sequence, treatment may be included as fixed effects.

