## 2.2 Study Population

Adult male healthy volunteers with a target of 50% of subjects in each of the following cohorts:

- Cohort A: Non morbidly obese men: BMI <40
- Cohort B: Morbidly Obese men: BMI ≥40

Inclusion Criteria:

- Adult Male Patients ≥18 years old
- Male anatomy at time of enrollment
- Ability to speak and understand English
- Willing to comply with all study procedures in the protocol
- Able to independently void urine
- Provision of signed and dated informed consent form

Exclusion Criteria:

- Urinary incontinence which does not allow the subject to spontaneously void
- Frequent episodes of bowel incontinence
- Has Urinary Retention
- Has any irritation, wound, open lesion, at the application site, on the genitalia, perineum, or sacrum
- Recent surgery of the external urogenital tract, penis, or pubic area
- Not able to comply with study procedures independently without required assistance
- Any other condition that, in the opinion of the investigator, would preclude them from participating in the study

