## 2.3 Randomization and Blinding

Subjects will be randomized using a block size of 4 and using a 1:1 ratio to one of the two treatment sequences. Subjects randomized to Sequence 1 will use PureWick MEC first, followed by Sage PrimoFit. Subjects randomized to Sequence 2 will use Sage PrimoFit first, followed by PureWick MEC. Randomization will be stratified by cohort. Cohort A consists of non-morbidly obese subjects (BMI < 40). Cohort B consists of morbidly obese subjects (BMI ≥ 40). The randomization schedule is created using R (R Core Team, 2021). Randomization seed is specified in the R script.

The investigational site will receive a set of randomization envelopes for each cohort that are numbered in sequential order. Within each randomization envelope, a treatment sequence assignment card will be enclosed, containing the sequence number and device to be used for each void. The randomization envelopes are to be opened in sequential order (as noted on the envelope) and are to be opened only when all inclusion/exclusion criteria are met.

The Investigator and Sponsor will know which device the participant is being treated with at any given time. Participants will remain blinded to treatment order until the study is complete.

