#### 5.2.3 Secondary Endpoint with Hypothesis Test

This secondary endpoint will be evaluated against the following hypotheses, in the ITT Subpopulation:

**H0:** Capture rate of PureWick™ Male (system) = Capture rate of established comparator (Stryker/ Sage PrimoFit™)

**H1:** Capture rate of PureWick™ Male (system) ≠ Capture rate of established comparator (Stryker/ Sage PrimoFit™)

A two-sided paired t-test will be used to test the hypotheses and p-value will be derived. A p-value  $< 0.05$ , combined with a capture rate in favor of PureWick™, indicates that PureWick™ is superior to PrimoFit™ in terms of urine capture, in patients who are unable to use traditional sheath style condom catheters.

An exploratory analysis will be performed using regression, where subject may be included as the random effect, and period, sequence, treatment may be included as fixed effects.

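### The primary paired t-test is valid and correctly powered, but it leaves out the randomised sequence and the BMI stratum; fitting both is a cheap, low-severity improvement

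*SAP*

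**What the plan says.** **Allocation.** SAP 2.3: "Subjects will be randomized using a block size of 4 and using a 1:1 ratio to one of the two treatment sequences", and "Randomization will be stratified by cohort". The cohorts are BMI below 40 and BMI 40 or more. SAP 2.2 plans "Adult male healthy volunteers with a target of 50% of subjects in each of the following cohorts".

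**Primary test.** SAP 5.2.2 (and protocol 10.5): "A two-sided paired t-test will be used to test the hypotheses and p-value will be derived". No period, sequence or cohort term enters it. An exploratory regression follows, in which "period, sequence, treatment may be included as fixed effects". Protocol 10.4.2 is firmer and commits to evaluating period and sequence effects by descriptive statistics and regression. BMI cohort is in no model in the available text. The table shells in SAP Appendix 1 are not available and may hold summaries by cohort.

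**Secondary test.** SAP 5.2.3: "This secondary endpoint will be evaluated against the following hypotheses, in the ITT Subpopulation". These are the men judged unable to use sheath-style catheters. The test is again a paired t-test, with the same open-ended exploratory regression.

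**Sample size.** SAP 2.4 gives 90% power with 44 men for a mean difference of half the SD of the paired difference. Its example reads "if the standard deviation of paired difference in capture rate is 10" per cent, with a 5-point difference. On enrolment: "Approximately 50 subjects will be enrolled to obtain 44 evaluable subjects".

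**The concern.** In a two-period crossover, a systematic difference between the first and second void enters the within-subject difference with opposite signs in the two sequences. The paired t-test leaves that spread in its standard error. With balanced sequences the estimate is unaffected, but the test becomes conservative and gives up some power. If the evaluable men are not balanced, the estimate also shifts. A device effect that differs between BMI cohorts is likewise left in the error. A BMI effect common to both devices cancels.

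A period effect is plausible but not established. Protocol 4.1 and 7.5 require a bladder-volume scan only before Void 2. The second device goes on after the first has been removed, and protocol 2.3.1 describes both as adhering to pelvic skin. Protocol 6.5.1 itself says the design allows carryover, period and sequence effects to be evaluated.

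At stake are a little power, protection against an uneven evaluable split, and a reader's ability to judge the subpopulation result, where sequence is not balanced by design.

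**Working it through.** **Inputs.** From SAP 2.4: n = 44 evaluable, two-sided alpha 0.05, difference 5, SD 10, about 50 enrolled. From SAP 2.3: 1:1 sequences, blocks of 4, two strata. Assumed: period effects p of 2, 3 and 5 points (Void 1 minus Void 2), a device-by-cohort gap of 5 or 10 points, and normal differences.

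**1. The plan's own figure.** Noncentrality 0.5 × √44 = 3.317 on 43 df gives power 90.0%. The stated power is correct.

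**2. The alternative.** For each man let D = PureWick minus PrimoFit, and fit D = μ + p·s + γ·(c − mean of c) + error, with s = +1 or −1 for sequence and c for cohort. Test μ on 41 df. With cohort centred, and balanced across the sequences, Var(μ̂) = (σ²/n) × n²/(4·n₁·n₂).

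**3. Cost when neither factor matters** (paired t-test 90.0%).

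| Evaluable split | Variance factor | Model power |
|---|---|---|
| 22:22 | 1.000 | 89.9% |
| 24:20 | 1936/1920 = 1.008 | 89.7% |
| 26:18 | 1936/1872 = 1.034 | 89.0% |

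26:18 is the extreme if exactly 50 are randomised. A cohort is at most 2 out of balance, and only when its size leaves remainder 2 on division by 4. If the two sizes sum to 50, either one leaves 2 and the other 0, or both are odd and at most 1 out each. The total imbalance is therefore at most 2, or 26:24. Six losses, all from the smaller sequence, give 26:18. Other totals can start up to 4 apart.

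Cohort must be centred. With a 30:14 cohort split, centring keeps 89.9%, but ±1 coding gives 85.5% because it estimates an equally weighted cohort average.

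**4. Gain, balanced, total SD 10** (residual variance 100 − p² − (gap/2)²).

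| Assumed effect | Paired | Model |
|---|---|---|
| Period 2 | 90.4% | 91.1% |
| Period 3 | 91.0% | 92.4% |
| Period 5 | 92.9% | 96.2% |
| Cohort gap 5 | 90.8% | 91.7% |
| Cohort gap 10 | 92.9% | 96.2% |

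The paired test's type I error is about 4.5%, 4.0% and 2.4% at period effects of 2, 3 and 5; the model holds 5.0%. If the residual SD is held at 10 instead, the paired test has about 89.4%, 88.3% and 85% power against about 90% for the model.

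**5. Evaluable split 26:18, no device difference, total SD 10.** The paired estimate shifts by p × (26 − 18)/44, which is 0.36, 0.55 and 0.91 points. False wins in the direction of the shift are about 4.1%, 4.7% and 5.7% by simulation. Direct integration (normal mean, noncentral chi-square variance) gives 3.9%, 4.7% and 5.8%. Nominal is 2.5%.

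**6. Subpopulation, assumed n = 12, residual SD 10, no device difference.** The shift is p × (n₁ − n₂)/12. At p = 5 it is 1.7 points for 8:4 and 2.5 points for 9:3.

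| Split | False PureWick wins, p = 2 | p = 5 |
|---|---|---|
| 8:4 | 3.7% | 5.1% |
| 9:3 | 4.7% | 9.1% |

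These are for the direction that favours PureWick. At p = 5 the opposite direction gives 0.4% and 0.2%. The chance of the favouring direction is 19% (coin-toss splits) or 11% (12 men drawn from 12:12) for 8:4 or worse, and 7.3% or 2.0% for 9:3 or worse. Averaged over splits at p = 5, two-sided type I error is 5.0% or 4.0%.

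**The case against.** The strongest reply is that nothing is wrong with the plan. The test is valid, the power figure reproduces, and under the SAP's total SD of 10 the balanced paired test never falls below 90%. The larger gains need a period effect as big as the device effect itself, or a cohort gap of 10 points, and no document supports either. The cost at 26:18 (1.0 point) exceeds the balanced gain at a 2-point period effect (0.7). Pairing already removes any BMI effect common to both devices, and protocol 4.2 introduces the cohorts to describe anatomical differences, not to reduce variance. Protocol 10.4.2 and the exploratory regression partly cover the issue. The subpopulation, where imbalance is likeliest, would lose real power by adjustment: at n = 12, a true difference of 10 and no period effect, 88% falls to 84% at 8:4 and 77% at 9:3.

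Most of this stands and sets the severity. It does not remove the point. The model holds its level at any evaluable split, which the paired test does not once a period effect exists. The promised evaluation also has no fixed model behind it. The subpopulation argument is why its confirmatory test should stay as planned.

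A reader might infer that the paired t-test is invalid, or that the subpopulation test inflates type I error. The documents support neither. Blocked 1:1 allocation keeps the randomised sequences close to balance, where the test is at worst conservative. In the subpopulation the distortion depends on the realised split and averages out.

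**Conclusion.** The point holds as a low-severity improvement to a valid analysis. The primary test omits both factors by which the trial randomises. Including them costs about 0.1 point of power when balanced and about 1 point at the 26:18 extreme. The benefit is conditional: a modest gain in power, and correct one-directional error under an uneven split, but only if a period effect or device-by-cohort difference exists. The documents do not establish one. In the subpopulation, an uneven split could move the result either way, and no fixed model would show by how much.

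The sizes rest on assumed effects, on the stated SD convention (total SD 10 for the primary unless noted, residual SD 10 for the subpopulation), on an assumed subpopulation of 12, and on normal differences although capture rate is bounded.

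**What to change.** **SAP 5.2.2 and protocol 10.5.** Make the primary test the intercept of a linear model on the within-subject differences (PureWick minus PrimoFit) in men with both voids evaluable. Code sequence ±1 and centre BMI cohort at its sample mean, so that cohort adjustment leaves the target as the mean difference in the analysed men. Keep the paired t-test as a sensitivity analysis. Report the device difference with a 95% CI by BMI cohort. State that the sequence term captures period and any carryover together.

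**SAP 5.2.3.** Keep the paired t-test as the confirmatory test. Replace the optional terms with one fixed sensitivity model with sequence coded ±1, reported with the number of men per sequence. If only one sequence is represented, say so and omit the model.

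**Cost.** Wording only, with no new data and two degrees of freedom in the primary test. The subpopulation test keeps its power. Because the sponsor is not blinded, the change should be made before capture rates by device are seen, and in any case before database lock.

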#### 5.2.3 Secondary Endpoint with Hypothesis Test

This secondary endpoint will be evaluated against the following hypotheses, in the ITT Subpopulation:

**H0:** Capture rate of PureWick™ Male (system) = Capture rate of established comparator (Stryker/ Sage PrimoFit™)

**H1:** Capture rate of PureWick™ Male (system) ≠ Capture rate of established comparator (Stryker/ Sage PrimoFit™)

A two-sided paired t-test will be used to test the hypotheses and p-value will be derived. A p-value  $< 0.05$ , combined with a capture rate in favor of PureWick™, indicates that PureWick™ is superior to PrimoFit™ in terms of urine capture, in patients who are unable to use traditional sheath style condom catheters.

An exploratory analysis will be performed using regression, where subject may be included as the random effect, and period, sequence, treatment may be included as fixed effects.

#### 5.2.4 Secondary Endpoint without Hypothesis Test

Summary statistics will be provided for

- Overall Comfort score on a 5-point Likert scale (brief questionnaire) for each device, and
- Ease of use by HCP in placing the MEC (brief questionnaire).

## 6 Summary of General Study Data

Appendix 1 includes table and listing shells for general study data.

## 7 Safety Analysis

Appendix 1 includes listing shells for AE and SAE.

## 8 Interim Analysis Plan

Not applicable.

## 9 References

None.

## 10 SAP Revision History

Version Number	Rationale for Change	Section or Page Affected	Description of Change
1.0	Original SAP		

## **11 Appendix**

### **11.1 Appendix 1 – Tables, Figures and Listing Shells**
